### **2.2.3. Toxicology**

A toxicology program has been conducted with ONCT-534 to support the Phase 1/2 clinical study and was comprised of exploratory single- and repeat-dose studies, maximum tolerated dose (MTD)/14-day-dose range studies, and definitive 28-day toxicology studies in 2 mammalian species (CD-1 mice and Beagle dogs) using the clinically relevant route (oral) and schedule (daily) of administration.

Findings in the male reproductive tract included decrease of prostatic secretions, decreased prostatic weights, and increased vacuolation of Sertoli cells. Findings were reversible after 28 days. Given the intended therapeutic effect of ONCT-534 as an ARSI, these findings in the male reproductive tract of ONCT-534-treated mice and dogs are considered to be associated with the primary pharmacodynamic effects of the molecule.

Findings in the liver included increased mean liver weight, minimal oval cell hyperplasia, and minimal to moderate centrilobular hepatocyte hypertrophy. There were no clinical pathology correlates. Findings were partially reversible after 28 days.

Findings in the kidney included minimal to moderate glomerulopathy, minimal or slight tubular degeneration, minimal or slight hyaline casts, minimal to moderate tubular regeneration, minimal to slight tubular vacuolation and minimal or slight tubular pigment. Findings were partially reversible after 28 days.

In 28-day definitive toxicity studies, ONCT-534 did not demonstrate seizurogenic potential at mean  $C_{max}$  exposures up to 18,800 ng/mL in mice and 3,570 ng/mL in dogs.

Overall, the findings observed reported in nonclinical toxicity studies were manageable and reversible.

#### **2.2.3.1. Photoreactive Potential**

Based on an initial assessment of photoreactive potential, ONCT-534 was found to absorb light at 290 nm, i.e., within the 290 and 700 nm range of natural sunlight. Therefore, the potential photo-safety risk to subjects treated with ONCT-534 will be managed by the use of light protective measures (see Section 6.2.3).

### **2.3. Clinical Experience with ONCT-534**

There have been no previous studies of ONCT-534 in human subjects.

### **2.4. Risk/Benefit Assessment**

#### **2.4.1. Known or Potential Risks**

ONCT-534 has not yet been administered to humans. Therefore, the potential human risks are based on findings from 28-day toxicity studies in mouse and dog.

Target organs identified histopathologically in the 28-day toxicity studies include the kidney, liver and prostate gland in mice and the testis, kidney, and liver in dogs. Given the intended therapeutic effect of ONCT-534 as an ARSI, the microscopic findings in the male reproductive tract of ONCT-534-treated mice and dogs are considered to be associated with the primary pharmacodynamic effects of the molecule and are therefore relevant to human risk. The nature of the microscopic findings in the kidney and liver were distinct in both species and likely represent chemical (versus target-mediated) toxicity. While clinical pathology correlates were not identified for any anatomic pathology findings in the kidney and/or liver findings, all findings were considered non-adverse and, with the exception of oval cell hyperplasia in the liver of dogs, were fully reversible upon cessation of dosing.

Seizures are known to occur in patients receiving the approved ARSIs, enzalutamide, apalutamide, and darolutamide. Seizures occurred in 0.4% to 0.6% of patients receiving apalutamide ([ERLEADA](#)), enzalutamide ([XTANDI](#)), and darolutamide ([NUBEQA](#)). In patients with predisposing factors, seizures were reported in 2.2% of patients receiving enzalutamide.

#### **2.4.2. Known or Potential Benefits**

ONCT-534 has not yet been administered to humans. Therefore, the potential benefits of ONCT-534 are based on its mechanism of action and nonclinical findings with ONCT-534 in tumor models.

As previously stated in Section 2.1.1, despite the availability of therapeutic strategies for advanced CRPC, including ARSIs such as enzalutamide, apalutamide, and darolutamide, 70% of patients develop resistance in 1 to 2 years after treatment initiation. The most common reasons for resistance to the ARSIs are AR gene amplification, mutations in the LBD, and the expression of AR splice variants that lack part or all of the LBD (Krause, 2023).

As previously stated (see Section 2.2.1), in nonclinical studies, ONCT-534 has demonstrated activity in several models resistant to approved ARSIs (Ponnusamy et al., 2019).

### 2.4.3. Assessment of Potential Risks and Benefits

ONCT-534 has not yet been administered to humans. Therefore, the overall assessment of potential benefit/risk is based on nonclinical findings from pharmacology studies, the definitive 28-day toxicity studies in mouse and dog, and risks described for other molecules in the class.

Since potential effects were observed in liver and kidney, subjects with moderate and severe renal or hepatic impairment will initially be excluded from the Phase 1/2 clinical study. In addition, all subjects will be monitored closely for changes in liver and kidney function in clinical studies with ONCT-534.

Considering the potential for other ARSIs to be associated with seizures, subjects with central nervous system (CNS) metastases or a history of seizure will initially be excluded from the study.

Overall, given the nature of the patient population and the limited number of subjects to be exposed in Phase 1 (n = 27) and Phase 2 (n = 32), clinical investigation of ONCT-534 is warranted in adult subjects with relapsed or refractory (R/R) histologically confirmed mCRPC resistant or refractory to at least one next-generation ARSI.

## 3. STUDY OBJECTIVES

### 3.1. Phase 1

Primary Objectives:

- To assess the safety, tolerability, and dose-limiting toxicity (DLT) of ONCT-534 at escalating doses.
- To determine the MTD of ONCT-534 and inform the 2 dose levels or schedules to be tested in Phase 2.

Secondary Objectives:

- To assess the preliminary antitumor activity of ONCT-534.
- To assess the PK of ONCT-534.

Exploratory Objectives:

- To assess the pharmacodynamics of ONCT-534
- To correlate PK/pharmacodynamics with clinical outcomes.

### 3.2. Phase 2

#### Primary Objectives:

- To assess the safety and tolerability of ONCT-534.
- To compare 2 dose levels or schedules of ONCT-534 and select the optimal dose for further study.
- To assess the preliminary antitumor activity of ONCT-534.

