### **9.1.2. Phase 2 Dose Expansion**

In the Phase 2 portion of the study, up to 16 evaluable subjects will be randomized into each of 2 expansion dose cohorts and evaluated for efficacy using a Simon 2-stage minimax design to exclude a response rate of < 10%, where response is defined as having  $\geq 50\%$  reduction in PSA. The hypothesized response rate under treatment is  $\geq 40\%$  and will be evaluated using a one-sided type I error rate of 0.025 with 80% power. A total of 9 subjects per dose level will be randomly assigned in Stage 1. If at least 2 responses of  $\geq 50\%$  reduction in PSA are observed, the dose level will proceed to Stage 2. If at least 5 responses are observed in a total of 16 subjects per dose level, the null hypothesis will be rejected.

Randomized dose assignment will proceed when both cohorts are open for enrollment. If one of the dose levels is closed due to safety findings or lack of efficacy findings, or is paused until Stage 1 efficacy is observed, non-randomized assignments may proceed within the open dose level expansion cohort. This hypothesis will require a dose cohort total of 16 for a Phase 2 Dose Expansion study total of 32 subjects.

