### 9.5.2. Analysis of Simon 2-stage Design

The Phase 2 Dose Expansion portion of the study will consist of 2 dose cohorts. Subjects will be assigned randomly to each Phase 2 cohort, evaluating a dose or schedule chosen by the SRC based on their evaluation of safety data and any PK, pharmacodynamics, and efficacy data obtained during the Phase 1 Dose Escalation portion of the study. Approximately 32 evaluable subjects are anticipated to enroll in Phase 2, with up to 16 subjects randomly assigned each of the 2 dose cohorts. There will be 9 subjects assigned in the first stage of the Simon 2-stage design, with the remaining 7 subjects also being assigned within a dose cohort to complete the second stage of the Phase 2 Dose Expansion portion of the study.

After evaluating the first 9 subjects for efficacy (defined as a reduction in PSA levels of  $\geq 50\%$ ) in Stage 1 (including subjects who received the same dose during Phase 1 of the study), the study will be terminated if  $\leq 1$  subject responds. If the study progresses to Stage 2, an additional 7 subjects will be treated, for a total of up to 16 evaluable subjects per dose cohort. If at least 5 subjects respond out of the total 16 within a dose cohort, there will be demonstration of efficacy of ONCT-534 within the population for this dose cohort and the corresponding null hypothesis will be rejected. Additional subjects may be enrolled to account for unevaluable subjects.

Randomized dose assignment will proceed when both cohorts are open for enrollment. If one of the dose levels is closed due to safety findings or lack of efficacy, or is paused until Stage 1 efficacy is observed, non-randomized assignments may proceed within the open dose level expansion cohort.

The expected maximum sample size in Phase 2 is 32.

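### Comparing the two doses is a primary Phase 2 objective, but the protocol specifies no between-dose estimate and no randomized, concurrent set in which to make one

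*Combined protocol and SAP*

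**What the plan says.** Section 3.2 makes it a primary Phase 2 objective "To compare 2 dose levels or schedules of ONCT-534 and select the optimal dose for further study". The Synopsis repeats this.

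The only Phase 2 hypothesis is in Section 9.1.2, to which Section 9.3.1.2 refers back. It is a Simon two-stage test of each dose separately against a 10% rate of at least 50% PSA reduction. It "will be evaluated using a one-sided type I error rate of 0.025 with 80% power", with a hypothesized rate of at least 40%. The decision rule is: "If at least 5 responses are observed in a total of 16 subjects per dose level, the null hypothesis will be rejected".

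Four other provisions bear on who is in each cohort and how the results are shown:

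- **Stage 1 membership.** Section 9.1.2 says "A total of 9 subjects per dose level will be randomly assigned in Stage 1". Section 9.5.2 describes the first 9 as "including subjects who received the same dose during Phase 1 of the study".
- **Non-random assignment.** If one dose is closed or paused, "non-randomized assignments may proceed within the open dose level expansion cohort" (Section 9.1.2; Section 9.5.2 has the same provision).
- **Analysis sets.** Section 9.2 groups the efficacy-evaluable subjects by dose received. It defines no randomized set and no concurrently randomized set.
- **Reporting.** Section 9.4 plans descriptive summaries by dose level, with 95% confidence intervals where appropriate, and leaves further detail to a SAP to be finalized before database lock. Sections 9.5.3 to 9.5.5 define PSA, tumor response and safety summaries within each group.

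**The concern.** A primary objective that names a comparison needs a stated quantity and a stated set of subjects. The protocol gives neither. The two Simon tests say whether each dose beats 10%; they do not say how the doses differ, and if both pass they leave nothing prespecified to separate them.

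The natural substitute is to read the two cohort totals side by side. Under the stated grouping those totals may hold three kinds of subject: those randomized while both doses were open, those treated earlier at the same dose in Phase 1, and those assigned to the only open dose. The last two groups have no concurrent randomized counterpart. A difference between totals can then reflect who was enrolled and when, rather than dose, which is the problem that randomizing was meant to remove. At stake is the choice of dose for further study.

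**Working it through.** **1. The plan's own figure.** Inputs from Section 9.1.2: continue with at least 2 of 9, reject with at least 5 of 16, null rate 10%, alternative 40%. The probability of rejecting at true rate p is the sum over x = 2 to 9 of P(X1 = x | 9, p) × P(X2 ≥ 5 − x | 7, p).

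- At p = 0.10: 0.0159, within the one-sided 0.025.
- At p = 0.40: 0.815, against the stated 80%.

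The design reproduces, and an exhaustive search confirms 16 as the smallest total that meets these limits. Both error rates belong to a single dose tested against 10%. Neither refers to a contrast between doses.

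**2. Can the two tests stand in for a comparison?** At p = 0.30 the same formula gives 0.529. Treating the doses as independent:

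- Both truly 40%: both pass with probability 0.815 × 0.815 = 0.66.
- 40% and 30%: both pass with probability 0.815 × 0.529 = 0.43.

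In those trials the tests give the same answer for both doses.

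**3. How far can randomization be diluted?** Section 9.1.1 allows up to 12 Phase 1 subjects at a dose level. Under Section 9.5.2 they could fill all 9 Stage 1 places at that dose, leaving 16 − 9 = 7 randomized at most. Under Section 9.1.2 all 9 would be randomized. The two sections cannot both govern Stage 1.

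**4. Precision of a difference.** The documents give no between-dose effect, so 40% and 20% are assumptions. The Wald 95% half-width is 1.96 × √[(0.40 × 0.60 + 0.20 × 0.80)/n] = 1.96 × √(0.40/n).

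| Subjects per dose | Situation | Half-width |
|---|---|---|
| 16 | both cohorts full and fully randomized | 31 points |
| 9 | only Stage 1 concurrent | 41 points |
| 7 | 9 places per dose filled from Phase 1 | 47 points |

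**5. How often both doses reach 16.** Under the Stage 1 rule, applied to each dose as in Section 9.1.2:

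- A 40% dose stops with probability 0.6⁹ + 9 × 0.4 × 0.6⁸ = 0.071.
- A 20% dose stops with probability 0.8⁹ + 9 × 0.2 × 0.8⁸ = 0.436.
- Both continue with probability 0.929 × 0.564 = 0.52.

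So the 31-point figure applies to about half of trials at these rates.

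Steps 4 and 5 measure imprecision, which would exist with perfect randomization. The bias from mixing subjects cannot be calculated from the documents, because they do not say how many Phase 1 or non-randomly assigned subjects to expect or how they would differ.

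**The case against.** The strongest defense is that this is a small, estimation-oriented study in which by-dose summaries plus committee judgment are a recognizable way to choose a dose. Section 9.4 plans the summaries, Section 9.5.4 gives exact intervals for response rates, and Section 10.1.4 puts the question of the recommended dose to the Safety Review Committee (SRC). Detail is deferred to a SAP whose text is not in the document, so one can say only that no comparison appears in the protocol. This stands. It does not close the gap: the estimate and comparison set for a primary objective are more than detail, and the protocol requires the SAP only before database lock, in a study for which it describes no blinding.

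Three stronger readings are tempting, and the documents do not support them.

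- **That the randomization is not used.** It governs allocation whenever both cohorts are open. What is missing is an analysis that contrasts the groups it creates.
- **That Phase 1 and non-randomized subjects will be pooled.** The provisions are conditional. Phase 1 subjects count only at the same dose, and Section 9.5.2 names them for Stage 1; non-random assignment may occur only if the other dose is closed or paused. Section 9.4 may also keep Phase 1 and Phase 2 apart in the descriptive tables.
- **That the primary objective gets no answer.** It gets descriptive summaries and a committee decision. It does not get an estimated difference.

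Nor is the sample size wrong for its single-dose purpose. A formal test between doses would be unrealistic: at 16 v 16 and 20% v 40%, two-sided Fisher power at 0.05 is about 13%.

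**Conclusion.** The concern holds as a gap in specification. The protocol sets a between-dose comparison as a primary objective, provides no between-dose estimate, and defines no set of subjects in which randomization protects such an estimate. If the permitted additions to the cohorts occur, side-by-side totals can carry selection and calendar-time bias, with no stated rule for separating the subjects. Sections 9.1.2 and 9.5.2 also conflict on Stage 1.

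The half-widths of 31, 41 and 47 points, and the 52% chance that both doses reach 16, rest on assumed rates of 40% and 20%. The half-widths also use the Wald approximation with equal numbers per dose; the 52% assumes independent cohorts and the stop rule applied dose by dose. They show what a comparison could deliver and do not measure the bias. The change is worth making because it is cheap and bears on a primary objective; the Simon tests are unaffected by the added estimate.

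**What to change.** In Section 9.5.2:

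1. Prespecify the between-dose difference in the PSA response rate, and in key safety and tolerability rates (for example Grade 3 or higher adverse events and discontinuations), each with a 95% interval suited to small samples, such as a score interval.
2. Define the comparison set as subjects newly enrolled in Phase 2 and randomized while both cohorts were open. Exclude Phase 1 subjects, including those re-assigned at random to a Phase 2 dose under Section 4.1.3, who have already been exposed to the drug and would otherwise pass a filter based on randomization alone.
3. Show Phase 1 subjects and non-randomly assigned Phase 2 subjects separately.
4. State that the comparison is for estimation and that dose selection stays with the SRC.
5. Reconcile Sections 9.1.2 and 9.5.2 on who makes up the 9 Stage 1 subjects.

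The cost is a few sentences and one added table on data already collected, with no added subjects. The downside is that the stated precision will look modest, and more so if a cohort stops or pauses after Stage 1.

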#### Secondary Objectives:

- To correlate antitumor activity of ONCT-534 with AR phenotype.
- To assess the pharmacodynamics of ONCT-534.

#### Exploratory Objectives:

- To correlate PK/pharmacodynamics with clinical safety and efficacy outcomes.

## 4. STUDY DESIGN

### 4.1. Overall Study Design

Study ONCT-534-101 is a Phase 1/2, multi-center study to evaluate the safety, tolerability, antitumor activity, and PK of ONCT-534, a novel DAARI that inhibits AR activity and induces AR degradation in multiple nonclinical models of prostate cancer resistant to current ARSIs, in subjects with R/R histologically confirmed mCRPC who have relapsed or are refractory to at least one next-generation ARSI, such as enzalutamide, darolutamide, apalutamide, or abiraterone.

A study schema is provided in Section 1.2. and a detailed schedule of activities in Table 1.

All subjects will undergo the following:

- **Screening:** Determining eligibility, starting up to 28 days prior to treatment.
- **Treatment Period:** ONCT-534 will be self-administered orally once daily at the same time every day, at least 2 hours after food and one hour before food. ONCT-534 will be provided as scored tablets with strengths of 40 mg and 200 mg. Dose escalation in Phase 1 will begin at a dose of 40 mg per day.
- **End of Treatment (EOT) Visit:** The EOT Visit will be performed after approximately 2 years of treatment (at Week 108). If the subject stops treatment prior to Week 108, an EOT Visit should be performed as soon as practical, ideally within 72 hours of early termination from the study. The subject will be followed for 30 days after the last dose of ONCT-534 to monitor for adverse events (AEs). All subjects will be contacted 30 days after their last dose of ONCT-534 for a final safety interview.

- **Extended Treatment:** Subjects continuing to benefit from ONCT-534 at the end of the study may be offered continuing treatment under a separate Extended Treatment study.

#### **4.1.1. Phase 1 Dose Escalation**

The Phase 1 portion of the study will use an adaptive Bayesian Optimal Interval (BOIN) Design (Liu et al., 2014; Yuan et al., 2016). The anticipated number of subjects in the Phase 1 portion is approximately 27 evaluable subjects, in 5 planned dose cohorts. The primary objectives are to assess the safety, tolerability, and DLT of ONCT-534 at escalating doses and to determine the MTD of ONCT-534 to inform the 2 dose levels or schedules to be tested in Phase 2. DLT will be assessed during the first 28 days of study treatment. DLT is defined in Section 8.3.7. The DLT assessment period will be from ONCT-534 administration on Day 0 through Day 28 and be based on DLT-evaluable subjects (Section 9.2).

The ONCT-534 dose levels to be tested will initially be 40, 80, 160, 300, and 600 mg orally once per day. Additional dose levels (e.g., intermediate levels, or larger or smaller doses) or dosing schedules (e.g., twice daily) may be studied at the discretion of the Safety Review Committee (SRC) based on their review of safety data and any PK, pharmacodynamics, and efficacy data.

The AR phenotype and AR levels of each subject's disease will be evaluated pre-treatment and on study based on analyses of circulating tumor DNA (ctDNA), circulating tumor cells, archival or fresh biopsy tissues, or on-study tumor biopsies (Section 8.1.10 and 8.1.11).

The SRC will review the safety, PK, pharmacodynamics, and preliminary efficacy data from each dose cohort in Phase 1 and will make the decision to escalate to the next dose level based upon their review of the data. The SRC will also propose the 2 dose levels or schedules to be tested in the Phase 2 expansion portion based upon available safety data, and any PK, pharmacodynamics, and efficacy data.

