### 1.3. Schedule of Assessments

**Table 1: Schedule of Assessments**

Protocol Section ↓	Study Day/Week →	Screening	D0	D1	D14	D15	D28/W4	W6	W8	W12	W16	W20	W24	Q12W	W108 a	EOT a
	Visit Window (Days) →	-28 to -1			±4		±4	±4	±7	±7	±7	±7	±7	±7	±7	
8.1.1	Eligibility assessments	X														
8.1.2	Physical examination	X	X		X		X	X	X	X	X	X	X	X	X	X
8.1.3	Weight; vital signs	X	X		X		X	X	X	X	X	X	X	X	X	X
8.1.4	12-Lead Electrocardiogram	X	X		X			X		X					X	X
8.1.5	Clinical chemistry	X			X		X	X	X	X	X	X	X	X	X	X
8.1.6	Prostate-specific antigen	X					X		X	X	X	X	X	X	X	X
8.1.7	Clinical hematology; coagulation	X			X		X	X	X	X	X	X	X	X	X	X
8.1.8	Urinalysis	X					X			X			X	X	X	X
6.2.1	ONCT-534 administration in clinic		X	X	X	X	X		X	X						
8.1.9	Blood for pharmacokinetics	X	X	X b	X	X b	X		X	X						
8.1.10	Blood for biomarkers	X					X			X					X	X
8.1.11	Tumor biopsy (encouraged but optional)	X								X						
8.2	CT, chest/abdomen and pelvis c	X								X			X	X	X	
8.2	Bone scan c	X								X			X	X	X	
8.3	Adverse events	X	X	X	X	X	X	X	X	X	X	X	X	X	X d	X d
6.3	Concomitant medications	X	X	X	X	X	X	X	X	X	X	X	X	X	X	X

CT = computed tomography; D = day; EOT = End of Treatment; Q12W = every 12 weeks; W = week.

a EOT Visit at 108 weeks, or if subject discontinues prior to Week 108.

b D1 and D15 pharmacokinetic sample must be collected 24 ± 2 hours from the ONCT-534 dose on D0 and D14, respectively.

c Confirmatory scan(s) required at least 4 weeks after partial response or complete response is first documented.

d All subjects will be contacted 30 + 7 days after their last dose of ONCT-534 for a final safety interview.

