### 8.3.7. Definition of Dose-Limiting Toxicity

DLT will be defined as any of the following attributed to ONCT-534 treatment occurring in the first 28 days of ONCT-534 treatment:

1. Any death not clearly related to the underlying disease or extraneous causes (e.g., accident or trauma).
2. Dose delays due to an AE lasting more than 14 days.
3. Non-hematologic toxicity:
  - a. Grade 3 or higher.
  - b. Hy’s law cases ([Appendix 1](#)).
  - c. AST or ALT  $> 8 \times$  ULN.
  - d. AST or ALT  $> 5 \times$  ULN lasting more than 14 days.
4. Hematologic toxicity
  - a. Grade 4 neutropenia or thrombocytopenia lasting more than 7 days.
  - b. Grade 3 or higher thrombocytopenia with clinically significant bleeding.
  - c. Neutropenic fever.

The definition of DLT will exclude:

- Grade 3 nausea/vomiting or diarrhea for less than 72 hours with adequate antiemetic and other supportive care.
- Grade 3 fatigue for less than 1 week.
- Grade 3 or higher BUN or electrolyte abnormality that lasts up to 72 hours, is not clinically complicated, and resolves spontaneously or responds to conventional medical interventions.
- Grade 3 or higher amylase or lipase that is not associated with symptoms or clinical manifestations of pancreatitis.

During the DLT evaluation period (Day 1 through Day 28 of study treatment) of the dose escalation cohorts, AEs identified as DLTs are required to be reported by the Investigator to the Sponsor immediately (no more than 24 hours after learning of the event), who will notify the SRC. Refer to Section 8.3.9 and Section 8.4 for recording and reporting procedures.

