### **8.3.8. Time Period and Frequency for Collecting AE and SAE Information**

Investigators will seek information on AEs at each subject contact. All AEs will be collected and recorded in the subject's medical record and on the Adverse Event eCRF as follows:

- From signing of ICF until first dose of study treatment: All SAEs, AEs due directly to study-related procedures/assessments, and AEs leading to subject/study discontinuation.
- From first dose of study treatment through 30 days after the last dose of study treatment OR initiation of subsequent anti-cancer therapies, whichever occurs first: All AEs and SAEs.
- Ongoing AEs/SAEs that are definitely, probably, or possibly related to study drug, should be followed until resolution or stabilization to  $\leq$  Grade 2, or returned to baseline status.

See Section 8.3.9 for instructions on recording AEs and SAEs, including abnormal laboratory values; pre-existing medical conditions; hospitalization; and disease progression, relapse, or disease-related death.

For each AE recorded on the Adverse Event eCRF, the Investigator will make an assessment of seriousness (Section 8.3.6), severity (Section 8.3.4), and causality (Section 8.3.5).

SAEs are required to be reported by the Investigator to the Sponsor immediately (i.e., no more than 24 hours becoming aware of the event). See Section 8.4 for reporting instructions.

Investigators are not obligated to actively seek AE or SAE collection after conclusion of the study participation. However, if the Investigator learns of any SAE, including a death, at any time after a subject has been discharged from the study and he/she considers the event to be reasonably related to the study drug or study participation, the Investigator must promptly notify the Sponsor.

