## **9.2. Populations for Analysis**

The DLT-evaluable Population is defined as all subjects in the Phase 1 Dose Escalation part of the study who receive ONCT-534 and either complete the 28-day DLT observation period or discontinue the study early due to a DLT. Subjects will be grouped by the dose received.

The Safety Population is defined as all subjects who receive at least one dose of ONCT-534. Subjects will be grouped by the ONCT-534 dose received at study entry.

The Efficacy-evaluable Population is defined as all subjects who receive ONCT-534 and complete at least one post-treatment disease assessment and do not discontinue due to clinical evidence of disease progression without documentation prior to obtaining post-treatment disease assessment. Subjects will be grouped by dose received.

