## 9.5. Analysis of Endpoints

### 9.5.1. BOIN Design Implementation and Assessment of MTD

A BOIN design will be employed to find the MTD. The BOIN design is implemented in a simple way incorporating features of the traditional 3+3 design but is more flexible and possesses superior operating characteristics that are comparable to those of more complex model-based designs, such as the continual reassessment method (Zhou et al., 2018). Operating characteristics will be detailed in the SAP.

[figure not shown]
The target DLT rate for the MTD is  $\phi = 0.3$  and the maximum sample size is 27, using an accelerated titration design for the first 2 dose levels. DLTs are defined in Section 8.3.7, and those DLTs that occur within the first 28 days of treatment will be used for dose finding. As shown in

Figure 1, the BOIN design uses the following rule once it has moved from a cohort size of 1 to 3, optimized to minimize the probability of incorrect dose assignment, to guide dose escalation/de-escalation:

- If the observed DLT rate at the current dose is  $\leq 0.236$ , escalate the dose to the next higher dose level;

- If the observed DLT rate at the current dose is  $> 0.359$ , de-escalate the dose to the next lower dose level;
- If the above criteria are not met, remain at the current dose until a maximum of 12 subjects have been enrolled and treated at that dose level.

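### The Day 28/Week 4 visit may be held on Day 24, so a Phase 1 subject may be counted DLT-free with up to 4 days of the DLT period unexamined

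*Combined protocol and SAP*

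**What the plan says.** **The DLT period.** The protocol states it in three ways. Section 4.1.1 says: "The DLT assessment period will be from ONCT-534 administration on Day 0 through Day 28". Section 8.3.7 has: "During the DLT evaluation period (Day 1 through Day 28 of study treatment". Section 9.5.1 says "those DLTs that occur within the first 28 days of treatment will be used for dose finding".

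**The visits.** In Table 1 (Section 1.3) the window row reads ±4 days for D14, D28/W4 and W6, and ±7 days from W8. Physical examination, chemistry and hematology are marked at D28/W4 and again at W6, with nothing scheduled between.

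**Who is counted.** Section 9.2 makes a Phase 1 subject DLT-evaluable if he receives drug and must "either complete the 28-day DLT observation period or discontinue the study early due to a DLT". It names no exam, lab or contact that has to fall at or after the end of the period.

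**Other routes by which an event can surface.** Section 8.3.8 says "Investigators will seek information on AEs at each subject contact", and AEs are collected from first dose onward. Sections 8.3.7 and 8.4 require a DLT to be reported within 24 hours of the investigator learning of it. Sections 8.1.5 and 8.1.7 allow unscheduled labs when there is a clinical reason.

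**The concern.** D28/W4 is the only scheduled visit that can close the DLT period, and its window opens before that period ends. A site that sees the subject on Day 24 has followed the protocol. He can then stay on treatment to Day 28, satisfy Section 9.2 and enter the tally, although nothing was scheduled on Days 25 to 28.

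Some DLT criteria in Section 8.3.7 are laboratory findings that may cause no symptoms: AST or ALT above 8 times ULN, Hy's law, and other Grade 3 or higher chemistry not covered by the exclusions. This is a first-in-human study (Section 2.3). Liver and kidney are named as nonclinical target organs (Section 2.4.1), and Section 2.4.3 promises close monitoring of both.

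The error has one direction. A missed DLT can only lower the count compared with Table 5, so it can only favour escalation or staying over de-escalation.

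**Working it through.** **The plan's own figures.** The inputs are the target rate φ = 0.3 and the 0.95 elimination cutoff with a uniform prior (Section 9.5.1). The documents do not give the BOIN design alternatives, so I assume the usual defaults φ1 = 0.6φ = 0.18 and φ2 = 1.4φ = 0.42.

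- Escalation boundary: ln[(1−φ1)/(1−φ)] / ln[φ(1−φ1)/(φ1(1−φ))] = 0.2365 (plan: 0.236).
- De-escalation boundary: ln[(1−φ)/(1−φ2)] / ln[φ2(1−φ)/(φ(1−φ2))] = 0.3585 (plan: 0.359).
- With elimination from the Beta(1+y, 1+n−y) posterior, all 36 cells of Table 5 reproduce.

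The decision rule is therefore sound. The question is whether the count fed into it is complete.

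**Dates.**

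- D28/W4: 28 − 4 = Day 24 to 28 + 4 = Day 32.
- Week 6: 42 − 4 = Day 38 to 42 + 4 = Day 46.
- From a Day 24 visit to the next scheduled labs: 38 − 24 = 14 to 46 − 24 = 22 days, all after the DLT period.
- Unexamined part of the DLT period: 28 − 24 = 4 days, or 27 − 24 = 3 days if the first 28 days means Days 0 to 27.

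**Effect on the escalation decision.** The documents give no timing of DLTs and no share that would go undetected, so this is an illustration. Assume a constant hazard over 28 days, every visit on Day 24, and every DLT up to the visit seen. With true rate p, the rate seen by Day 24 is 1 − (1−p)^(24/28). If a share s of the later DLTs is missed, the observed rate is q = p − s × (p − rate seen by Day 24). Table 5 escalates at 0/3, with probability (1−q)³, and at no more than 1/6, with probability (1−q)⁶ + 6q(1−q)⁵.

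For p = 0.30: 1 − 0.70^(24/28) = 0.2634. With s = 1, (1 − 0.2634)³ = 0.3997. With s = 0.25, q = 0.30 − 0.25 × 0.0366 = 0.2909.

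| True rate | Late DLTs missed | Observed rate | P(0/3) | P(≤1/6) |
|---|---|---|---|---|
| 0.30 | none | 0.3000 | 0.3430 | 0.4202 |
| 0.30 | a quarter | 0.2909 | 0.3566 | 0.4402 |
| 0.30 | all | 0.2634 | 0.3997 | 0.5024 |
| 0.40 | none | 0.4000 | 0.2160 | 0.2333 |
| 0.40 | a quarter | 0.3886 | 0.2285 | 0.2514 |
| 0.40 | all | 0.3546 | 0.2689 | 0.3106 |

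On the Days 0 to 27 reading (exponent 24/27), a true rate of 0.30 with all late DLTs missed is seen as 0.2717, and P(0/3) is 0.3863.

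**The case against.** The strongest reply is that DLT ascertainment does not depend on the visit alone. AEs are collected continuously, DLTs carry a 24-hour reporting duty, and unscheduled labs are allowed. A symptomatic DLT on Days 25 to 28 that is reported counts in full. That stands, and it limits the exposure to silent laboratory events and to events the subject does not volunteer in time. It does not remove it: the reporting clock starts only when the investigator learns of the event, and a silent event gives no reason for an extra draw.

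A reader might infer more than the documents support, in four ways.

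- *That a Day 24 visit itself makes a subject DLT-free.* It does not. Section 9.2 still requires the 28-day period to be completed. The documents permit the outcome but do not prescribe it.
- *That a silent Grade 4 cytopenia could be missed this way.* Section 8.3.7 requires it to last more than 7 days. One starting after Day 24 cannot reach that by Day 28, unless onset alone is what has to fall in the period.
- *That the accelerated-titration trigger is equally exposed.* Under Sections 8.3.1 and 8.3.2, laboratory changes without clinical significance are not AEs, so a silent Grade 2 value would often not be a new Grade 2 AE.
- *That the next cohort will be dosed higher before the previous one has been examined.* That depends on when the SRC takes its tally. The SRC Charter (Section 10.1.4) is not in the document and may require end-of-period data. The implementation steps in Section 9.5.1 also break off at step 3 in the copy read. SRC decisions are guided by the BOIN rule and do not follow Table 5 automatically.

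**Conclusion.** The gap is real and modest. The date arithmetic is firm: a compliant visit can leave the last 4 days of the DLT period (3 on the narrower reading) without a scheduled exam or labs, and no text in the copy read closes it.

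The size of any bias cannot be taken from the documents. At a true rate of 0.30 it runs from no change in P(0/3), through about 1 percentage point if a quarter of late DLTs are missed (34% to 36% after rounding), to about 6 points (34% to 40%). The upper end stacks a constant hazard, every visit on Day 24 and every late DLT missed, and should not be read as an expected value. The direction is certain: a missed event favours escalation.

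**What to change.** Add a footnote to Table 1: for Phase 1 subjects in the DLT period, the D28/W4 window is 0/+4 days, so that the exam, chemistry, hematology and AE review close the DLT period before the subject enters the BOIN tally. Phase 2 keeps ±4 days. Reconcile Sections 4.1.1, 8.3.7 and 9.5.1 so that the DLT period is stated in one way.

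The cost is a Phase 1 footnote in a table that serves both phases, and a visit, and possibly an SRC decision, that may come a few days later. No visit or procedure is added. Repeating labs and AE review after an early visit would also close the gap, but it adds a procedure whenever the visit was early, so the window change is preferable.
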